## STUDY SUMMARY

Title	A clinical study to compare caries detection in children between the iTero Element 5D system (NIRI) and bitewing radiographs (BWR) as a diagnostic aid for the detection of primary carious lesions above the gingiva.
Purpose	A comparison of caries detection in pediatric population between the iTero Element 5D system and bitewing radiographs as a diagnostic aid for the detection of primary carious lesions above the gingiva.
Design	This is a non-significant risk, single site, prospective clinical study. The study will be conducted in the department of pediatric dentistry of the faculty of dental medicine of the Hebrew university, Israel
Objectives	
Primary Objective:
 
The objective of this study is to compare caries detection in pediatric population between the iTero Element 5D system and bitewing radiographs as a diagnostic aid for the detection of primary interproximal carious lesions above the gingiva.
 
Secondary Objectives:
 
 
To compare users' experience using a qualitative questionnaire
 
To compare carious lesions depth as appears in NIRI and BWR images to clinical depth observed during caries excavation
 

Primary Endpoint	
Primary effectiveness endpoint measures:
 
The iTero 5D will be non-inferior to BWR in detecting the existence of primary interproximal caries lesions above the gingiva in pediatric population.
 
Secondary effectiveness endpoint
 
 
Qualitative users' feedback relating to: chair time, the ability to capture tooth surfaces (reachability), patient's experience (gag reflex, discomfort) will be collected through questionnaire
 
Lesion depth will be documented in cases where caries debridement was conducted. NIRI and BWR images will be compared to the clinical findings
 

Study Device	iTero Element 5D
Eligibility Criteria	
Inclusion Criteria:
 
A subject will be considered eligible if the following inclusion criteria are fulfilled:
 
 
Ages 4-9 years
 
Subjects scheduled for bilateral BWR as part of their standard of care
 

## Clinical Study Protocol 1

	

• Subjects with a recent bilateral BWR which were obtained up to 14 days prior to study visit

 
Exclusion Criteria:
 
A subject will be considered ineligible if any one of following exclusion criteria are fulfilled:
 

• Subjects who have been diagnosed with epilepsy

• Subjects with a known allergy to latex or plastic

• Subjects with allergies to any dental or oral health products

• Subjects who have undergone a dental treatment since the acquisition of the recent bilateral BWR

Sites	This study will be conducted in the department of pediatric dentistry of the Hadassah Medical Center, Faculty of Dental Medicine, Hebrew University of Jerusalem, Israel
Sample Size	70 subjects
Length of Study	Approximately 6 months

# Clinical Study Protocol 1

## 1. INTRODUCTION AND BACKGROUND

### 1.1 BACKGROUND

In 2007, Cadent Ltd. (now Align Technology, Ltd.) started marketing intraoral scanner systems to the dental industry. iTero scans have been used in more than 3.6 million restorative crowns, bridges, and custom implant abutment cases and more than 13.5 million iTero orthodontic scans, for a total of 17.1 million scans.

The iTero Element 5D system is an intraoral scanner with near-infrared imaging (NIRI) technology.

Near-infrared Imaging (NIRI) is a nonionizing imaging technology that leverages differences in scattering and absorption of near-infrared light depending on the degree of tooth mineralization. In vivo and vitro studies investigating the iTero Element 5D system for the detection of caries have yielded encouraging results.

[figure not shown]
This prospective study is designed to compare caries detection in pediatric population between the iTero Element 5D system and bitewing radiographs as a diagnostic aid for the detection of primary interproximal carious lesions above the gingiva without using harmful radiation.

## 2. DESCRIPTION AND INDICATIONS FOR USE

### 2.1 DEVICE DESCRIPTION

The iTero Element 5D (figure 1) is an intra-oral optical scanner for acquiring digital impressions. The system digitally captures the 3D geometry and color of the patient's intraoral dental structures using a proprietary optical, non-contact, focus detection technique using a Class 1 laser technology.

[figure not shown]
# Clinical Study Protocol 1

**Figure 1. The iTero Element 5D**

The iTero Element 5D incorporates near-infrared illumination capabilities used to provide a near-infrared image of the teeth enabling the detection of both occlusal and proximal caries, at the various stages, ranging from initial enamel caries to established caries reaching the DEJ.

# Clinical Study Protocol 1

[figure not shown]

**Figure 2.** The NIR Cam mode. NIR images are displayed on the main screen while a color image is displayed in the View Finder window

NIR functionality is implemented by using 850nm wavelength LEDs. Incorporating both the NIR images and the color images captured by the system can aid in the detection of caries (Figures 3 and 4).

**Figure 3.** Color Image as captured by the iTerio Element

**Figure 4.** NIRI image demonstrating two proximal carious lesions (Red circles)

# Clinical Study Protocol 1

## 2.2 iTero Element 5D Intended Use

The iTero Element 5D system is indicated for intra oral scanning. NIRI technology of the iTero Element 5D aids in detection and monitoring of interproximal caries lesions above the gingiva without using harmful radiation.

## 3. STUDY PURPOSE AND OBJECTIVES

### 3.1 STUDY OBJECTIVES

The objective of this study is to scan subjects intraorally with iTero Element 5D system and compare caries detection in pediatric population to common practice (bitewing radiographs) as a diagnostic aid for the detection of primary interproximal carious lesions above the gingiva.

### 3.2 SECONDARY OBJECTIVES:

- To compare users' experience using a qualitative questionnaire
- To compare carious lesions depth as appears in NIRI and BWR images to clinical depth observed during caries excavation when indicated.

## 4. STUDY DESIGN

### 4.1 OVERVIEW OF STUDY DESIGN

This is a non-significant risk, single site, prospective study to be conducted in the department of pediatric dentistry of the Hadassah Medical Center, Faculty of Dental Medicine, Hebrew University of Jerusalem, Israel. Subject participation will require one visit during which consent, screening, enrollment, and imaging will be performed. An additional follow-up call to the Investigator will take place a month later to review patient records and capture any clinical information recorded since last trial visit if a treatment was planned.

Each subject will be assigned a unique ID number that will link to their data. De-identified data sets will be used for analysis.

Clinical and diagnostic methods to be used during this study are those that are routinely used in the diagnosis of caries in this site, which include bitewing radiographs (BWR). This standard of care is provided for all site’s patients, including the patients who don’t participate in this clinical study.

A standard set of BWR for subjects ages 4-9 years will be taken to include the complete dentition of the subjects. Any recent bilateral BWR which were obtained up to 14 days prior to study visit may be used. **No additional x-ray should be taken for the sole purpose of this trial.**

In addition to the routine clinical diagnostics, the subjects will be scanned using the 5D system. The investigator will capture a full arch scan of the maxillary arch and mandibular arch of each subject with the iTero Element 5D system. For each subject, the Investigator will grade carious lesions in the BWR and Element intra-oral scan according to ADA staging guidelines. The results will be documented using

# Clinical Study Protocol 1

Caries Evaluation Forms. The Investigator will assess and document the findings of each diagnostic test separately before reviewing the next test.

In cases where caries debridement indicated, carious lesion depth will be documented during and compared to NIRI and BWR images. **All treatment decisions will be made according to the standard of care in the clinic and no treatment will be conducted for the sole purpose of the study.**

The study will include an interim analysis to assess the iTero Element 5D system useability among the first 20 pediatric subjects. Based on the findings' evaluation, modifications in the study protocol for the remaining 50 subjects will be considered.

Once images from the iTero Element 5D system and the bilateral BWR are obtained, the subject will have completed the study visit.

Data regarding caries treatments that were executed in accordance with the clinic standard of care during a follow-up period of 1 month post study visit will be captured in the CRF.

Duration of the study is estimated to be six months.

All participating doctors and designated office coordinators will be trained on the clinical study protocol and Good Clinical Practices (GCP).

## 4.1.1 MATERIALS

See section 2.

## 4.1.2 METHODS

### 4.1.2.1 INCLUSION CRITERIA

A subject will be considered eligible if the following inclusion criteria are fulfilled:

- Ages 4-9 years
- Subjects scheduled for bilateral BWR as part of their standard of care
- Subjects with a recent bilateral BWR which were obtained up to 14 days prior to study visit

### 4.1.2.2 EXCLUSION CRITERIA

A subject will be considered ineligible if any one of following exclusion criteria are fulfilled:

- Subjects who have been diagnosed with epilepsy
- Subjects with a known allergy to latex or plastic
- Subjects with allergies to any dental or oral health products
- Subjects who have undergone any dental treatment since the acquisition of the recent bilateral BWR

### 4.1.2.3 SCHEDULE OF STUDY VISITS

Subject participation will require one patient visit during which consent, screening, enrollment, imaging and study exit will be completed.

# Clinical Study Protocol 1

- **Initial Visit**

1. Review inclusion and exclusion criteria (Eligibility criteria)
2. Inform subject and obtain written assent form
3. Enrollment Form
4. Intraoral Scan: Subjects will be scanned intraorally using the iTero Element 5D system.
5. Acquisition of recent BWR data.
6. Caries Evaluation Form

## **4.1.3 END STUDY**

The End of Study occurs when a subject has completed all study-related procedures and follow-up. When all subjects have completed the study, a report will be written concluding the findings from the study. Subsequent clinical evaluation and treatment, if indicated will be performed after study completion by each patient's dentist.

## **4.2 NUMBER OF SUBJECTS/ ASSIGNMENT TO TREATMENT GROUPS**

70 subjects will be enrolled in one site.

The study will include an interim analysis to assess the iTero Element 5D system useability among the first 20 pediatric patients. Based on the findings' evaluation, modifications in the study protocol for the remaining 50 subjects will be considered.

## **4.3 SITE**

This study will be conducted by [name] in the department of pediatric dentistry of the Hadassah Medical Center, Faculty of Dental Medicine, Hebrew University of Jerusalem, Israel. The Investigator will be proficient with the use of the iTero Element 5D system.

## **4.4 SUBJECT WITHDRAWAL**

Subjects have the right to withdraw from the study at any time for any reason. The Investigator may withdraw the subject at any time for any reason. If any subject withdraws or is withdrawn from the study, any non-study records that were taken while the subject was enrolled in the study will not be shared with the study Funder and there will be no requirement to continue treatment according to this protocol. Withdrawal from the study will not result in any penalties and will not preclude or interfere with the Investigator's treatment of the subject outside of the study. Additional subjects may be enrolled to substitute for any withdrawn subjects until the study target enrolment is reached.

The schedule of all study activities and procedures is provided in Table 1. No additional invasive or other burdensome interventions in comparison to the standard care will be performed.

Data will be entered into a database, located on a secure server. Each subject will be assigned a unique ID number which will link to their data. Data will be examined for completeness and checked for accuracy. De-identified data sets will be used for analysis.

# Clinical Study Protocol 1

## 4.5 CLINICAL DATA MANAGEMENT CASE REPORT FORMS

The Case Report Forms (CRF) for this Study are as follows:

- Subject Enrollment Form
- Caries Evaluation Forms
- User experience questionnaire
- Data regarding caries extend observed during caries excavation
- Withdrawal Form (if applicable)
- Adverse Event Form (if applicable)
- Protocol Deviation Form (if applicable)

## 5. STATISTICAL AND ANALYTICAL PLANS

### 5.1 HYPOTHESIS

The test results can be summarized in the following 2x2 table:

	X-ray is the ground truth	
NIRI	Negative (no caries)	Positive (caries)
Negative (no caries)	$P_{00}$	$P_{01}$
Positive (caries)	$P_{10}$	$P_{11}$

Where  $P_{ij}$  = the percentage of tooth surfaces under certain condition out of all included surfaces.

As we are taking X-ray as the ground truth,  $P_{01}$  is the percentage of surfaces that can be detected as caries by X-ray but not NIRI (NIRI missed detection rate),  $P_{10}$  is the percentage of surfaces that can be detected by NIRI, but not X-ray (NIRI over detection rate). By showing that NIRI over detection rate ( $P_{10}$ ) is not less than NIRI missed detection rate ( $P_{01}$ ) by non-inferiority margin of  $M$ , we can conclude that NIRI is non-inferior than X-ray in detecting caries. Thus,  $P_{10}-P_{01}$  provides a measure for assessment of a non-inferiority between two procedures.

Null Hypothesis:  $P_{10}-P_{01} \leq -M$

Alternate Hypothesis:  $P_{10}-P_{01} > -M$

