### 5.2 ASSUMPTIONS

#### 5.2.1 Test results

By assuming:

1. 50% of the participants will have active caries
2. On average there are 1 carious surface per patient with active caries
3. there is minimum of 2 naïve IP surfaces per pediatric patient which may be captured in BWR

Approximately, out of all patients included in the trial, 1.8% of all tooth surfaces are carious and 98.2% of all tooth surfaces are non-carious.

# Clinical Study Protocol 1

Based on previous iTero 5D study, we can assume that for NIRI, the sensitivity for early enamel lesions is 0.51 and specificity is 0.90.

The assumed test results can be summarized as:

	X-ray is the ground truth	
NIRI	Negative (no caries)	Positive (caries)
Negative (no caries)	88.38%	0.88%
Positive (caries)	9.82%	0.92%

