## 5.3 SAMPLE SIZE

Sample size can be calculated from the sample size equation for comparing paired nominal data by using McNemar’s test:

$$n = \frac{[z_{\alpha}\sqrt{p_{01} + p_{10}} + z_{\beta}\sqrt{p_{01} + p_{10} - (p_{01} - p_{10})^2}]^2}{(p_{10} - p_{01})^2}$$

Similar formulae can be obtained for the one-sided non-inferiority test by substituting  $z_{\alpha/2}$ ,  $p_{10}$  with  $z_{\alpha}$  and  $p_{10} + M$ :

$$n = \frac{[z_{\alpha}\sqrt{p_{01} + p_{10} + M} + z_{\beta}\sqrt{p_{01} + p_{10} + M - (p_{01} - p_{10} - M)^2}]^2}{(p_{10} + M - p_{01})^2}$$

where significance level  $\alpha = 0.05$ , power  $1 - \beta = 0.8$ , non-inferiority margin  $M = 5\%$ , assumed detection rate  $p_{01} = 0.22\%$ ,  $p_{10} = 2.46\%$

The minimum sample size required is 89 surfaces. Assuming the drop off rate to be 30%, an additional 39 surfaces will be recruited, so the total number of surfaces needed for the clinical trial is 128. assuming a minimum of 2 naïve IP surfaces per paediatric patient.

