## 5.5 STATISTICAL ANALYSIS PLAN

Statistical tests will be performed to show comparison between iTero NIRI technology of the iTero Element 5D and bite-wing x-ray in detecting the existence of primary interproximal caries lesions above the gingiva

- Two-sided McNemar's Chi-square test to show if there is a statistically significant difference between the detection ability of the iTero NIRI technology of the iTero Element 5D and bite-wing x-ray
- Asymptotic Non-Inferiority test to show if the false positive (FP) rate ( $P_{10}$ ) is non-inferior than false negative (FN) rate ( $P_{01}$ ) with non-inferiority margin as 0.05, which means iTero NIRI technology of the iTero Element 5D is non-inferior than bite-wing x-ray in detecting primary interproximal caries
- One-sided binomial test to show if the false positive (FP) count ( $C_{10}$ ) is significantly higher than false negative (FN) count ( $C_{01}$ ), which indicates if iTero NIRI technology of the iTero Element 5D can detect more primary interproximal caries than bite-wing x-ray
- Kappa coefficient will be calculated to assess the agreement between two methods. (Moderate agreement (Kappa 0.41–0.60) is expected)

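### The primary rule P10 − P01 > −5% lets NIRI false positives cancel missed lesions, so it compares positive-call rates and cannot show non-inferior caries detection

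*Combined protocol and SAP*

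**What the plan says.** Section 5.1 sets up a 2x2 table of tooth surfaces, each cell a share of all included surfaces. It fixes the reference: "As we are taking X-ray as the ground truth". P01 is then the share that NIRI misses and P10 the share that NIRI over-calls. The null is P10 − P01 ≤ −M, with M = 5% (section 5.2.2). On rejection, "we can conclude that NIRI is non-inferior than X-ray in detecting caries".

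Section 5.5 repeats the rule with the error labels attached: "Asymptotic Non-Inferiority test to show if the false positive (FP) rate" is non-inferior to the false negative rate. It adds a one-sided binomial test of whether the false positive count exceeds the false negative count, "which indicates if iTero NIRI technology of the iTero Element 5D can detect more primary interproximal caries than bite-wing x-ray". A two-sided McNemar test is also listed, and "Kappa coefficient will be calculated to assess the agreement between two methods", with moderate agreement (0.41 to 0.60) expected.

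Section 5.2.1 assumes 1.8% of surfaces are carious and that "the sensitivity for early enamel lesions is 0.51 and specificity is 0.90". No success criterion is set for sensitivity or specificity.

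**The concern.** With BWR as the truth, a surface in the P10 cell has no caries and a surface in the P01 cell has a missed lesion. A detection claim needs P01 to be small relative to the lesions present, with P10 also limited. The rule instead credits P10 against P01, so a missed lesion on one surface is bought back by a false alarm on another.

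At a fixed miss rate, a less specific device is then more likely to succeed. A positive result would not establish the primary endpoint in section 5.4.1, which is non-inferior detection of interproximal lesions. The binomial result could also be reported as superior detection when, by the plan's own reference, the additional calls are errors.

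**Working it through.** **Inputs.** M = 5%, one-sided α = 0.05, and 89 surfaces (128 after 30% drop-off) come from sections 5.2.2 and 5.3. Prevalence 1.8%, sensitivity 0.51 and specificity 0.90 come from section 5.2.1.

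**The plan's figures reproduce.** Section 5.3 uses p01 = 0.22% and p10 = 2.46%, so p01 + p10 + M = 0.0768 and p10 + M − p01 = 0.0724. Then n = [1.645√0.0768 + 0.842√(0.0768 − 0.0724²)]² / 0.0724² = 88.5, which rounds up to the stated figure: "The minimum sample size required is 89 surfaces". The 2x2 table also reproduces: 0.018 × 0.49 = 0.88%, and 0.982 × 0.10 = 9.82%.

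**What the statistic measures.** P10 − P01 = (P10 + P11) − (P01 + P11) = P(NIRI positive) − P(BWR positive). In the plan's table:

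- P10 − P01 = 10.74% − 1.80% = +8.94 points, far above −5.
- Share of BWR lesions missed = 0.88/1.80 = 49%.
- Share of NIRI positives that are false by the plan's reference = 9.82/10.74 = 91%.
- Kappa: observed agreement is 0.8838 + 0.0092 = 0.8930. Chance agreement is 0.8926 × 0.9820 + 0.1074 × 0.0180 = 0.8785. Kappa = 0.0145/0.1215 = 0.12.

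**Probability of passing.** Set P01 = prev × (1 − sens) and P10 = (1 − prev) × (1 − spec). Enumerate all outcomes exactly for independent surfaces. A sample passes when (d + 0.05)/√[(p01 + p10 − d²)/n] > 1.645, where p01 and p10 are the observed proportions and d = p10 − p01. Samples with no discordant surface count as a pass.

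Direction of the rule at 25% prevalence. This assumes 0.5 lesion per child (half the children have caries, and "On average there are 1 carious surface per patient with active caries") over exactly 2 surfaces per child:

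| Sens | Spec | P10 − P01 | Pass, n = 89 | Pass, n = 128 |
|---|---|---|---|---|
| 0.80 | 0.98 | −3.5 | 0.20 | 0.20 |
| 0.80 | 0.90 | +2.5 | 0.64 | 0.78 |
| 0.80 | 0.80 | +10.0 | 0.95 | 0.99 |
| 0.51 | 0.90 | −4.75 | 0.06 | 0.06 |
| 0.51 | 0.60 | +17.75 | 0.96 | 0.99 |
| 0.50 (coin flip) | 0.50 | +25.0 | 0.995 | >0.999 |

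The direction does not depend on the variance estimate. At sensitivity 0.80 and n = 128, lowering specificity from 0.98 to 0.80 moves the pass probability from 0.13 to 0.99 with a score test, and from 0.08 to 0.98 with the null variance behind the section 5.3 formula. A device that flags every surface has P01 = 0, so its difference is never negative.

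At the plan's 1.8% prevalence and specificity 0.90, a device that finds no lesion at all scores 9.82 − 1.80 = +8.02 points. It passes with probability 0.989 (n = 89) or 0.999 (n = 128).

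**Binomial test.** For that same zero-sensitivity device, the exact one-sided test is significant in 83% of trials at n = 128.

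**The case against.** The best defence is that P10 − P01 is the ordinary paired contrast for two fallible tests. BWR is imperfect, so some P10 surfaces may be real lesions, and scoring NIRI only against BWR counts them as errors. That is fair as an argument for a different framing, but the plan chose the opposite one. Even with both methods treated as fallible, unverified extra calls cannot be counted as caries found, and the contrast still compares only call rates.

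Three points about the size do stand:

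- **The 1.8% results mix two defects.** P01 cannot exceed 1.8% there, so the difference cannot reach −5% whatever NIRI does. A device that flags nothing passes with probability 0.20 to 0.80, depending on n and the variance used. The 25% table is the cleaner evidence of offsetting.
- **25% is an upper bound.** The plan says at least 2 surfaces per child; 1.8% with 0.5 lesion per child would need about 0.5/0.018 = 28. At 25% and specificity 0.90, a zero-sensitivity device passes with probability below 0.001, and its expected difference clears −5% only if specificity is below 0.733.
- **The section 5.3 rates are on another scale.** They are about a quarter of the table cells (0.88/4 = 0.22; 9.82/4 = 2.455). For a zero-sensitivity device, p10 = 2.46% with P01 = 1.8% gives 0.84 (n = 89) and 0.92 (n = 128), and the binomial test is significant in 3% at n = 128. Quartering P01 as well, to 0.45%, gives 0.995, 0.999 and 13%.

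Other planned results would reveal gross over-calling: the two-sided McNemar test would show the imbalance and a low kappa would be visible. Neither is a success criterion. The debridement comparison (section 5.4.2) is secondary and reaches only treated lesions.

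**Conclusion.** The concern holds. Under the plan's own ground truth, the conclusion of non-inferior detection does not follow from P10 − P01 > −5%. The identity with the difference in positive-call rates is exact and needs no assumption about prevalence or clustering. At any prevalence below 100%, lower specificity moves the statistic towards success.

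The size does depend on assumptions. With 25% prevalence, sensitivity 0.80 and 128 independent surfaces, the pass probability rises from 0.20 to 0.99 as specificity falls from 0.98 to 0.80. At 1.8%, a device that detects nothing passes almost surely at specificity 0.90, partly because a 5-point margin on all surfaces cannot be breached there. Clustering within children would change these probabilities but not the direction. Because the fault lies in the primary conclusion and recurs in the binomial claim, it must be fixed before analysis.

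**What to change.** In sections 5.1 and 5.5:

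1. Base the detection conclusion on P01/(P01 + P11) among BWR-positive surfaces and P10/(P00 + P10) among BWR-negative surfaces, each with a patient-clustered confidence interval.
2. If a non-inferiority claim is kept, pre-set a limit for each proportion and require both to be met.
3. If P10 − P01 is retained, for example because both methods are regarded as fallible, drop the ground-truth and FP/FN labels and describe it only as a comparison of positive-call rates.
4. Restate the binomial conclusion as NIRI flagging more surfaces than BWR.
5. State the expected number of BWR-positive surfaces and the precision that follows.

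Items 1 and 3 to 5 are SAP wording and need no new data. Item 2 is not free, because the stated 80% power does not carry over. At 1.8%, 89 to 140 surfaces hold about 2 to 3 lesions. At 0.5 lesion per child, 70 children give about 35, and 0.51 ± 1.96√(0.51 × 0.49/35) is 34% to 68%. As an illustration, ±10 points would need 1.96² × 0.51 × 0.49/0.10² = 96 lesions, or 96/0.5 = 192 children. Both figures are before clustering. The sponsor must either re-size for that test or report the miss proportion as an estimate of low precision. A favourable result also becomes harder to obtain.
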